Official Study Title: Increasing Accuracy and Efficiency of Fidelity Measurement in CBT

Brief Title: Project FACTS (Fidelity Accuracy: Comparing Three Strategies)

NCT02820623

May 11, 2020

Executive Summary

1. Description of theory, methodology, intent of study

Our objective is to compare the accuracy, costs, and cost-effectiveness of three fidelity measurement methods to assess fidelity to cognitive-behavioral therapy for youth. We will randomize up to 170 therapists, implementing cognitive-behavioral therapy to 3 conditions: self-report, chart stimulated recall, and behavioral rehearsal (N = about 56 for each group). To calculate our outcomes of interest, each condition will be compared to the gold-standard fidelity measurement method, direct observation.

OBJECTIVES

Objective 1: To identify the most accurate fidelity measurement method.

Objective 2: To estimate the economic costs and cost-effectiveness of the fidelity measurement methods.

Objective 3: To compare stakeholders' motivation to use each method, as well as identify their perceived barriers and facilitators to use of each method.

This study will have a significant positive impact in two ways. First, it will validate fidelity measurement methods that can then be used by implementation scientists for research. Second, it will produce tools that can be used by community mental health clinics to monitor therapist fidelity, an indicator of therapy quality.

BACKGROUND

The significance of this study is its potential to reduce the research-to-practice gap by identifying accurate and cost-effective fidelity measurement methods that both researchers and stakeholders in community mental health clinics can use to monitor fidelity of evidence-based practices. This will allow for the public health impact of evidence-based psychosocial interventions to reach its potential. Specifically, we use the exemplar treatment, cognitive-behavioral therapy (CBT), an established evidence-based practice for a wide range of child and adult psychiatric disorders, to test the three fidelity measurement methods. The proposed research is based on a framework which identifies fidelity as a key implementation outcome.

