Therapist fidelity is frequently measured due to its mediating role between implementation of evidence-based practices and client outcomes. Fidelity can also be conceptualized as an indicator of quality of care, which is a priority for many national organizations such as the Institute of Medicine. Fidelity includes adherence (how closely the components of a protocol are followed) and competence (how skillfully the components are implemented and therapist responsiveness to the child). The gold-standard fidelity measurement technique is direct observation, which is infeasible in community agencies due to lack of recording devices, time, and trained coders. Community mental health clinics sorely need methods of measuring fidelity that are accurate and cost-effective. Accurate methods refer to those with strong reliability and validity, whereas cost-effective methods refer to those that can be used with the limited resources in routine practice settings while providing benefit.

Therapists' self-report of their own fidelity is easy to administer, brief, and low-cost. However, the correspondence between self-report and independent observers is low (e.g., kappa of .22 in one

study). Leading scholars have suggested that self-report is frequently inaccurate because self-report measures typically include many terms that are unfamiliar to therapists; and because therapists are not trained in rating their own behavior (i.e., how to rate high vs. low behavior). One way to address these concerns is to ensure that the operational definitions of each item are clear and to train therapists in how to rate their own behavior. Additionally, two innovative methods from the medical literature, chart-stimulated recall and behavioral rehearsal, hold promise for fidelity measurement. Chart-stimulated recall entails a brief interview with a clinician about the care provided to a client, while allowing the clinician to review the client's file to assist recall. Behavioral rehearsal refers to a simulated interaction between a clinician and another individual around treatment delivery. Our goal is to test the accuracy, costs, and cost-effectiveness of each of these three methods in comparison to direct observation.

STUDY SAMPLE AND DATA SOURCE

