Due to COVID-19, we have also decided to implement remote recruitment of therapists and clients. Research staff will recruit therapists by emailing them directly and introducing the study. If therapists are interested in participating in the study, research staff will consent therapists over the phone. Once consented, research staff will work with therapists to identify eligible clients using sequential sampling, which will ensure that we enroll clients receiving services across the treatment span. Therapists will introduce the study to eligible clients (and if necessary, guardians) via a virtual platform to obtain verbal consent (and if necessary, assent). If the client (and if necessary, guardian) are interested, research staff will enroll and consent clients through a virtual platform. Research staff will place the audio recorder next to the computer in a private room, press “record” on the audio recorder, close the door and leave the room. Therapists will notify the research staff through text message once the session is over. Youth will be paid with an electronic \$10 Amazon gift card for allowing their therapy session to be audio-taped.

All three conditions (described below) will be compared with direct observation (i.e., audio-recordings of each session). Therapists will be randomized to one of the three experimental measurement conditions. Therapists in the self-report condition will be asked to complete the self-report measure within 48 hours of the encounter, to ensure appropriate recall and also because that is typically when therapists are expected to complete their notes (personal communication, [name], Community Behavioral Health). Therapists in the other two conditions will

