All research activities for Aims 1 and 3, including data collection and engagement with human subjects, will be conducted by members of the University of Pennsylvania research team. All Aim 2 research activities will be conducted by members of the University of Pennsylvania research team as well as by co-investigators from Temple University.

ANALYSIS PLAN

All analyses are by intent-to-treat and will occur at the University of Pennsylvania Center for Mental Health Policy and Services Research under the direction of study biostatistician, [name]. Differences across the three arms of the study will be analyzed using SAS PROC MIXED. We will conduct three mixed-effects multivariate regression models. The dependent variable is difference in score between direct observation and the specific fidelity method under consideration. We will measure the dependent variables in three ways: raw score adherence, raw score competence, and total fidelity t-score (composite of adherence and competence raw score). We will conduct two sets of analyses. In the first set, the model will include two fixed effects (fidelity measurement method and site) and a random effect for therapist to account for the nesting

of patients within therapists. Our primary interest is in the beta coefficient for the fidelity measurement method, which tells us whether there is any difference in accuracy between the intervention arms. Our first hypothesis is that both chart-stimulated recall and behavioral rehearsal (i.e., total fidelity t-score) will be more accurate than self-report. Our second hypothesis is that chart-stimulated recall will capture adherence best. Our third hypothesis is that behavioral rehearsal will capture competence best. To test these hypotheses, we will use the model described above to conduct custom contrasts in the regression models to examine whether the mean of the dependent variable differs for each pair-wise comparison of our intervention arms. We will then repeat that analysis after transforming the dependent variable into t-scores to allow computation of standardized differences for each pairwise comparison, so that we can rank accuracy. The second model will include an additional fixed-effect term for time and an interaction (time X fidelity measurement method), allowing us to examine if there are changes in outcome over time by measurement method. This is important in case there are differential practice effects across condition over time.

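### The planned tests compare the three methods with one another on an apparently signed difference score, so they do not support a statement that any method is accurate or validated against direct observation, although the data would allow one.

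*Combined protocol and SAP*

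**What the plan says.** Several parts of the combined protocol and SAP describe a comparison with the gold standard. The impact paragraph under Objectives says of the study that "it will validate fidelity measurement methods that can then be used by implementation scientists for research". Background sets the goal as testing the accuracy, costs and "cost-effectiveness of each of these three methods in comparison to direct observation", and describes accurate methods as reliable and valid without giving a threshold. Procedures (Aim 1) states: "All three conditions (described below) will be compared with direct observation".

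The Analysis Plan then defines the outcome: "The dependent variable is difference in score between direct observation and the specific fidelity method under consideration". It does not mention an absolute or squared value. The quantities it names are:

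- the method coefficient, "which tells us whether there is any difference in accuracy between the intervention arms";
- custom contrasts to "examine whether the mean of the dependent variable differs for each pair-wise comparison of our intervention arms";
- a repeat on t-scores to obtain "standardized differences for each pairwise comparison, so that we can rank accuracy";
- a second model with time and time-by-method terms, "allowing us to examine if there are changes in outcome over time by measurement method".

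The three hypotheses are all relative: two methods against self-report, and one method best on each of adherence and competence. Objective 1 is also relative, since it asks which method is most accurate.

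**The concern.** Direct observation is half of the outcome, so each arm's model mean is its average departure from the gold standard. That mean carries the information about agreement on average, and a contrast between arms subtracts it out. The plan names no test or interval for it, no agreement statistic and no criterion.

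Two consequences follow. A null contrast cannot separate three methods that agree with direct observation from three that are wrong by the same amount. A shared error is plausible, because all three methods rest on the therapist's own report, recall or re-enactment of the session. Second, a contrast of signed means compares average bias. Over- and under-rating can cancel within an arm, and two methods with equal errors in opposite directions look different.

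At stake is the stated product: measures that researchers and clinics could adopt as validated. The method named best of the three might agree poorly with direct observation, and nothing in the planned tests would reveal it.

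**Working it through.** The documents give no SD, ICC, alpha, power or margin, so there is no figure of the plan's own to reproduce. What follows is illustrative.

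**Inputs.** From the documents: 3 sessions per therapist; up to 170 therapists, about 56 per arm (170/3 = 56.7); 405 encounters, which at 3 each is 135 therapists, or 45 per arm. Both 45 and 56 are used. Assumed: session-level SD of the difference = 1, therapist ICC 0.1 to 0.5, two-sided 5% tests, site effects ignored.

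**Shared bias cancels.** Write the mean difference in arm *k* as b + d_k, with b common to all arms. Any contrast is (b + d_j) − (b + d_k) = d_j − d_k, so b drops out. This is equally true if the outcome is a mean absolute difference.

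**Simulated check.** With b = 0.5 SD in every arm, 56 per arm and ICC 0.3, the SD of a therapist's mean is sqrt((1 + 2×0.3)/3) = 0.73. In 4,000 simulated trials, at least one of the three unadjusted contrasts was significant in 11.1%, all false positives. One-sample tests against zero were significant in all three arms in 99.7%.

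**What an arm mean would deliver.** SE = sqrt((1 + 2×ICC)/(3n)) and half-width = 1.96×SE. For n = 56 and ICC 0.3, SE = sqrt(1.6/168) = 0.098 and the half-width is 0.191. The last column is the power of a pairwise contrast between biases of +0.3 and −0.3 SD (difference 0.6, SE multiplied by sqrt 2).

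| n per arm | ICC | SE | 95% half-width | Power to detect 0.3 SD bias in one arm | Contrast power, +0.3 v −0.3 |
|---|---|---|---|---|---|
| 45 | 0.1 | 0.094 | 0.185 | 0.889 | 0.994 |
| 45 | 0.3 | 0.109 | 0.213 | 0.787 | 0.974 |
| 45 | 0.5 | 0.122 | 0.239 | 0.693 | 0.936 |
| 56 | 0.1 | 0.085 | 0.166 | 0.944 | 0.999 |
| 56 | 0.3 | 0.098 | 0.191 | 0.867 | 0.992 |
| 56 | 0.5 | 0.109 | 0.214 | 0.785 | 0.973 |

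The last column shows the ranking problem: two methods with equally large mean bias are declared different with probability 0.94 to 0.999.

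**A mean misses poor tracking.** Take method A as the observed score plus noise of SD 0.3, and method B as unrelated to the observed score but with the same mean and SD 1. With 56 independent values per arm and 2,000 simulations, the contrast rejected in 4.2%, about its nominal rate. The differences have SD 0.3 and sqrt(1 + 1) = 1.41. Limits of agreement would therefore be about ±1.96×0.3 = ±0.59 against ±1.96×1.41 = ±2.77 SD of the observed score, which separates the methods at once.

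**Dependence on a margin.** For two one-sided 5% tests at zero true bias, power = 2Φ(margin/SE − 1.645) − 1. Across the table's rows this is 0.90 to 0.998 at 0.4 SD, 0.59 to 0.94 at 0.3 SD, and 0 to 0.53 at 0.2 SD.

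**The case against.** The best defence is that the plan answers the question it sets. Objective 1 and all three hypotheses are comparative, and pairwise contrasts suit them. The Executive Summary introduces the gold-standard comparison as the way to calculate the outcomes, and the difference score does that, so the sentence in Procedures can be read as already met. Validation appears in an impact paragraph, not in an objective.

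Much of this stands. Neither the Executive Summary nor Procedures promises a hypothesis test for each arm, and the gap bears less on Objective 1 than on the broader claims. It does not rescue the validation claim or the Background goal of testing each method's accuracy. Nor does it rescue Objective 1 entirely, because signed means do not measure accuracy.

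Four stronger readings go beyond the documents:

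- A reader might infer that the trial cannot show any method to be accurate. Each arm's mean is estimable from the planned mixed model, and paired session scores exist for agreement statistics.
- A reader might infer that the plan at least ranks the methods soundly. With a signed outcome it ranks mean bias.
- A reader might infer that perfect methods and equally biased ones would give identical output. Only the contrasts lose the shared shift; arm means differ, and perfect methods would leave no residual variance.
- A reader might take an equivalence test on the mean, say at 0.4 SD, as validation. No passage supports that margin, a margin in SDs of the difference widens in raw points as a method gets noisier, and a method unrelated to the observed score could pass.

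**Conclusion.** The point holds as a gap between the claims and the prespecified analysis. The named tests are contrasts between arms plus time terms. The time main effect is not a contrast between methods, but it is not a test against direct observation either. None can detect a bias common to all arms and, if the difference is signed, none measures accuracy in the usual sense.

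The cancellation is algebra and needs no assumption. The ranking criticism rests on reading the outcome as signed, which is the natural reading but is not stated. The sizes rest on the assumed SD scale and ICC: half-widths of 0.17 to 0.24 SD per arm show that the missing estimate would be reasonably precise. Whether that suffices for an equivalence claim depends on a margin the documents do not give. At 0.2 SD it would not, since power is at most 0.53.

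**What to change.** Add to the Analysis Plan, before analysis:

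1. For each arm, on raw adherence and raw competence, report the site-adjusted least-squares mean of the signed difference from direct observation with its 95% CI. Do the same for total fidelity only if both scores are standardised to a common reference. If each were standardised to its own mean, the mean difference would be zero by construction.
2. For each arm, report a session-level agreement statistic: an ICC or limits of agreement, allowing for sessions nested in therapists.
3. State whether the modelled difference is signed or absolute, and base accuracy rankings on a measure in which over- and under-rating cannot cancel.
4. Call a method validated only where its results under items 1 and 2 meet a criterion in raw points, justified and fixed beforehand. Otherwise keep to relative conclusions, such as best of the three but not shown to agree with direct observation.

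The cost is SAP wording, a little more analysis, agreement on a criterion, and possibly a less favourable conclusion. No new data are needed.
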